## 5.4.2. Dose Interruptions or Decreases for Toxicity

### 5.4.2.1. Hematologic Toxicities

The following changes in hematologic values will be considered sufficient reason for dose interruption according to the guidelines in [Table 1](#).

**Table 1: Dose Interruptions for Hematologic Toxicities**

Parameter	Dose Reduction by 1 Dose Level If:	Hold If	Reinstitute Drug at 1 Dose Level Lower When Recovered to
Hematocrit (%)	< 35%	< 30%	≥ 35%
ANC ( $\times 10^9/L$ )	< $1.5 \times 10^9/L$	< $1.0 \times 10^9/L$	≥ $1.25 \times 10^9/L$
Platelet count ( $\times 10^9/L$ )	< $150 \times 10^9/L$	< $100 \times 10^9/L$	≥ $125 \times 10^9/L$

### 5.4.2.2. Nonhematologic Toxicities

Treatment with study drug should also be withheld for any  $\geq$  Grade 3 nonhematologic toxicity possibly, probably, or definitely related to treatment and only resumed after the toxicity returns to baseline.

Hematological and nonhematological toxicities should be reviewed by the investigator with the subject in person, by telephone, or by e-mail at least weekly. Drug may be withheld up to 4 weeks at a time up to a maximum of 8 weeks, but if hematology parameters do not return to the level for reinstating drug by that time, or if another nonhematological form of toxicity does not return to baseline grade, then the subject will be discontinued from the study. Erythropoietin is not allowed during the study.

Doses of both study drugs are titrated simultaneously following the guidelines in [Table 2](#).

**Table 2: Dose Levels for Ruxolitinib and Anagrelide and Dose Reduction/Restart Guidelines**

Dose Level	Ruxolitinib				Dose Level	Anagrelide			
	Week	Dose (mg)		Total Daily Dose (mg)		Week	Dose (mg)		Total Daily Dose (mg)
		AM	PM				AM	PM	
DL 4	W 2	25	25	50	DL 4	W 2	2.5	2.5	5
	W 1	25	25	50		W 1	2	2.5	4.5
DL 3	W 2	20	20	40	DL 3	W 2	2	2	4
	W 1	20	20	40		W 1	1.5	2	3.5
DL 2	W 2	15	15	30	DL 2	W 2	1.5	1.5	3
	W 1	15	15	30		W 1	1	1.5	2.5
DL 1 - STARTING DOSE		10	10	20	DL 1 - STARTING DOSE		1	1	2
DL -1	W 1	10	5	15	DL -1	W 1	1	0.5	1.5
	W 2	10	5	15		W 2	1	0.5	1.5
DL -2	W 1	5	5	10	DL -2	W 1	0.5	0.5	1
	W 2	5	5	10		W 2	0.5	0.5	1
DL -3	W 1	5	0	5	DL -3	W 1	0.5	0	0.5
	W 2	5	0	5		W 2	0.5	0	0.5

**5.4.2.3. Dose Reductions With Concomitant Cytochrome P450 Inhibitors**

**5.4.2.3.1. Cytochrome P450 3A4 Inhibitors**

Ruxolitinib is metabolized in the liver by the CYP-metabolizing enzyme system, predominantly by the 3A4 isozyme. With concomitant treatment of potent CYP3A4 inhibitors such as systemic ketoconazole (see [Appendix H](#)), plasma exposure of ruxolitinib increases by approximately 2-fold. Thus, a dose reduction of approximately 50% for study treatment is appropriate for subjects who take systemic ketoconazole or other potent CYP3A4 inhibitors systemically as concomitant medication. This dose reduction should be accomplished by reducing doses of ruxolitinib or ruxolitinib-placebo from BID to QD.

Potent inhibitors of CYP3A4 include systemic ketoconazole, posaconazole, voriconazole, clarithromycin, itraconazole, nefazodone, and telithromycin (see [Appendix H](#)). Dose reductions are not required for topical ketoconazole.

NOTE: Once the course of therapy using a CYP3A4 inhibitor has been completed, the subject may resume his/her previous BID dose regimen of study treatment beginning the next day.

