### 1.2.2. Nonclinical Drug Metabolism and Pharmacokinetics

After oral single-dose administration of ruxolitinib capsules in the fasted state, ruxolitinib was absorbed rapidly, typically attaining peak plasma concentrations within 1 to 3 hours after administration for all doses. After attaining the maximum plasma concentration (Cmax), the ruxolitinib plasma concentrations declined, with a mean terminal-phase disposition half-life of approximately 3 to 5 hours. The mean ruxolitinib Cmax and area under the curve (AUC) increased with approximately linear proportionality to dose for the entire dose range evaluated of 5 to 200 mg. There was no significant food effect on absorption or exposure.

Ruxolitinib is metabolized in the liver by the cytochrome P450 (CYP) metabolizing enzyme system, predominantly by the 3A4 isozyme. Systemic exposure of ruxolitinib was appreciably increased (AUC 2-fold higher) when given in combination with ketoconazole, a potent CYP3A4

inhibitor, with a similar effect observed on the pharmacodynamic (PD) activity (cytokine-induced STAT3 phosphorylation). Cytochrome P450 3A4 inducers significantly decreased the exposure to ruxolitinib, with essentially no difference observed on the PD activity (cytokine-induced STAT3 phosphorylation). This suggests that CYP3A4 induction with rifampin results in metabolism of ruxolitinib to active metabolites that also inhibit JAK.

Ruxolitinib was given as a single 25 mg dose to subjects with varying degrees of renal function (Study INCB 18424-142) and to subjects with varying degrees of hepatic dysfunction or with normal hepatic function (Study INCB 18424-137). Mild, moderate, or severe impairment of renal function had no statistically significant effect on PK or PD parameters; subjects requiring dialysis showed prolonged PD activity without a demonstrable effect on ruxolitinib clearance. The mean total AUCs of ruxolitinib were 87%, 28%, and 65% higher, respectively, in subjects with mild, moderate, and severe hepatic impairment than in subjects with normal hepatic function. Terminal half-life of ruxolitinib was increased in subjects with hepatic impairment by approximately 2-fold compared with healthy controls. The subjects with severe hepatic impairment showed modestly protracted PD activity compared with the other hepatically impaired subjects who displayed PD activity similar to the healthy controls.

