**5.4.2.3.2. Cytochrome P450 1A2 Inhibitors**

Anagrelide is metabolized at least in part by CYP1A2. Anagrelide is an inhibitor of cyclic AMP PDEIII. Thus, a dose reduction of approximately 50% for study treatment is appropriate for subjects who take potent CYP1A2 inhibitors systemically as concomitant medication (see [Appendix H](#)). This dose reduction should be accomplished by reducing doses of anagrelide or anagrelide-placebo from BID to QD.

NOTE: Once the course of therapy using a CYP1A2 inhibitor has been completed, the subject may resume his/her previous BID dose regimen of study treatment beginning the next day.

Investigators may refer to anagrelide label for further detailed information of potential interactions.

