### **5.4.4. Dose Modifications for Subjects Receiving Open-Label Treatment**

The dose increase, decrease, and discontinuation rules described in Sections 5.4.1, 5.4.2, and 5.4.3 will be followed for subjects receiving open-label anagrelide or open-label ruxolitinib. Table 2 should be used to identify dose levels for the individual study medications.

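### At dose level -3 the BID-to-QD rule for potent CYP3A4 inhibitors removes no dose, so ruxolitinib exposure approximately doubles; the CYP1A2 rule likewise removes no anagrelide there

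*Protocol*

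**What the plan says.** Protocol Section 5.4.2.3.1 gives the reason for a dose rule: with a potent CYP3A4 inhibitor, "plasma exposure of ruxolitinib increases by approximately 2-fold". It sets the target: "a dose reduction of approximately 50% for study treatment is appropriate for subjects who take systemic ketoconazole or other potent CYP3A4 inhibitors". It names one method: "This dose reduction should be accomplished by reducing doses of ruxolitinib or ruxolitinib-placebo from BID to QD". After the course, "the subject may resume his/her previous BID dose regimen of study treatment beginning the next day". Section 5.6.2 item 4 discourages potent inhibitors, does not ban them as a class, and treats the reductions in 5.4.2.3 as required.

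Section 5.4.2.3.2 has the same structure for potent CYP1A2 inhibitors: an approximately 50% cut, and "This dose reduction should be accomplished by reducing doses of anagrelide or anagrelide-placebo from BID to QD". Its NOTE on resuming treatment also assumes BID dosing.

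Table 2, "Dose Levels for Ruxolitinib and Anagrelide and Dose Reduction/Restart Guidelines", sets DL -3 at 5 mg AM and 0 mg PM for ruxolitinib, and 0.5 mg AM and 0 mg PM for anagrelide. Under Section 5.4.4 the modification rules "will be followed for subjects receiving open-label anagrelide or open-label ruxolitinib", so the rule also applies after Week 52.

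**The concern.** A rule that halves the dose by dropping one of two daily doses cannot work at a level with only one. Neither interaction section covers a subject who is already on once-daily dosing, and the two NOTEs suggest that DL -3 was overlooked.

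Dosing starts at DL 1, so a subject reaches DL -3 only after three net step-downs (DL -1, DL -2, DL -3). The gap therefore falls on subjects who could not be kept at a higher dose. They have little room left. Table 1 restarts a held drug one level lower, and Table 2 has no level below DL -3. Section 5.4.3.1 requires permanent discontinuation after certain recurrent hematologic toxicities if no lower restart dose is available. An avoidable drug interaction could thus contribute to ending treatment.

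Monitoring does not fully close the gap. The Synopsis (Core Treatment Period) requires extra hematology after a dose modification or as clinically indicated. At DL -3 the rule produces no modification, so only clinical judgment prompts the extra count. Scheduled counts are 4 weeks apart in Weeks 4 to 32, 2 weeks apart in Weeks 32 to 52, and 12 weeks apart in open label for subjects who do not cross over.

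**Working it through.** **Inputs**
- Exposure factor with a potent CYP3A4 inhibitor: F = 2 (Section 5.4.2.3.1, stated as approximate).
- Dose proportionality: Section 1.2.2 reports that ruxolitinib Cmax and AUC "increased with approximately linear proportionality to dose for the entire dose range evaluated of 5 to 200 mg".
- Morning and evening doses: Table 2. Ruxolitinib tablet strength: 5 mg (Section 5.2.1.1).

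**The plan's own figure.** The cut needed to keep exposure constant is 1 - 1/F = 1 - 1/2 = 50%, which agrees with the protocol.

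**What BID to QD delivers**
- Cut obtained = 1 - (dose kept / total daily dose).
- Exposure ratio = F x (dose kept / total daily dose).

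| Level | AM/PM (mg) | Total (mg) | Dose kept (mg) | Cut | Exposure ratio |
|---|---|---|---|---|---|
| DL 4 | 25/25 | 50 | 25 | 50% | 2 x 25/50 = 1.00 |
| DL 3 | 20/20 | 40 | 20 | 50% | 2 x 20/40 = 1.00 |
| DL 2 | 15/15 | 30 | 15 | 50% | 2 x 15/30 = 1.00 |
| DL 1 | 10/10 | 20 | 10 | 50% | 2 x 10/20 = 1.00 |
| DL -1 | 10/5 | 15 | 10 or 5 | 33% or 67% | 1.33 or 0.67 |
| DL -2 | 5/5 | 10 | 5 | 50% | 2 x 5/10 = 1.00 |
| DL -3 | 5/0 | 5 | 5 | 0% | 2 x 5/5 = 2.00 |

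The rule meets its target at five of the seven levels. DL -1 straddles the target (see the objection). At DL -3 it does nothing: the equivalent uninhibited dose is 2 x 5 = 10 mg/day, the total daily dose of DL -2.

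**Sensitivity.** The factor is only approximate. Over an assumed range of 1.8 to 2.2, the DL -3 ratio is 1.8 to 2.2, equivalent to 9 to 11 mg/day.

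**Anagrelide.** At DL -3 the cut is 1 - 0.5/0.5 = 0%. The protocol gives no exposure factor for CYP1A2 inhibitors, so no exposure ratio can be computed.

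**Is a 50% cut possible at DL -3?** One 5 mg tablet every other day averages 5/2 = 2.5 mg/day. The ratio is 2 x 2.5/5 = 1.00, or 0.9 to 1.1 over the assumed range. The supplied tablets are enough, but neither Table 2 nor Section 5.4.2.3 provides for this schedule.

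**The case against.** The strongest reply is that the investigator is not powerless. Section 5.4.1 allows dose decreases for safety at any time, and the Synopsis (Dose Titration Criteria) adds interruptions. Neither needs a count or symptom as a trigger. Section 5.4.2.3.1 states both the reason and the target, so an alert investigator could act when the inhibitor is started. Section 7.5.6 allows extra laboratory tests at the investigator's discretion, Table 1 thresholds still apply, and Section 5.4.2.2 asks for toxicity review at least weekly. All of this stands. It supplies authority to act, but no instruction at the one level where the written instruction fails, and no lower dose level to move to.

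It is also fair that the event is uncommon. It needs three net reductions and then a potent inhibitor that exclusion criterion 16 bars if its use is anticipated and Section 5.6.2 says to avoid. The gap therefore concerns unplanned courses.

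Two wider readings are tempting and should not be drawn.
- A reader might infer that DL -1 is wrong too, because the cut there is 33% or 67%. An exact half would be 7.5 mg, which 5 mg tablets cannot give as a single daily dose. The spread around an approximate target is a limit of tablet strength.
- A reader might infer that Section 5.4.2.3.1 licenses drugs on the QT list, because ketoconazole and clarithromycin appear both there and in Appendix J. Section 5.6.3 item 10 is an unconditional ban, and a site that obeys it complies with both sections. The other five inhibitors named in 5.4.2.3.1 are not on the Appendix J list, so the dose rule still has a purpose. A cross-reference would be a convenience only.

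**Conclusion.** The point holds for DL -3. The written rule gives a 0% cut where about 50% is intended. Ruxolitinib exposure rises to about twice its previous value, that of DL -2, in subjects already reduced to the lowest level. For anagrelide the finding is the 0% cut alone.

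This rests on the protocol's approximately 2-fold factor and on dose proportionality reported after single doses. The number of subjects affected is probably small and cannot be derived from the documents.

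A reader might infer that the gap exposes subjects to an untested dose or weakens the trial's main comparison. The documents support neither. Ten mg/day is a listed dose level and half the 20 mg/day starting dose, and the planned analysis, power and alpha are unchanged. This is a dosing instruction that fails at one level, is relevant to patient safety, and is cheap to correct. It should be corrected.

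**What to change.** 1. Add a DL -3 rule to Section 5.4.2.3.1: use a non-potent alternative. If a potent CYP3A4 inhibitor is unavoidable, give ruxolitinib or its placebo as 5 mg every other day for the course, or hold it if the investigator judges that safer.
2. Have the sponsor set the matching DL -3 rule for anagrelide or its placebo in Section 5.4.2.3.2, since the protocol gives no exposure factor from which to derive one.
3. Delete the word BID from the resumption NOTE in both sections, so that a subject returns to whatever regimen was in use before.

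The administrative cost is a protocol clarification and a site letter. There are clinical costs too. Alternate-day dosing is not a Table 2 level, and with an uninhibited half-life of about 3 to 5 hours (Section 1.2.2) it gives a less even exposure profile.

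A hold goes beyond the 50% target. Section 5.4.3.3 warns that symptoms may return over about a week after stopping. A hold also uses interruption time under Section 5.4.2.2 unless the text exempts it.

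A hold in Weeks 32 to 52 may also cost count control. Visits are 14 days apart with a window of 3 days either way (Section 7.6.1), so gaps run from 14 - 6 = 8 to 14 + 6 = 20 days. A 14-day hold can cover 0 to 2 visits and a 28-day hold 1 to 3, before any recovery time. SAP Section 7.2.3.1.1 defines five periods of seven visits, each needing at least six controlled visits. For a subject controlled at every other visit, one lost visit fails no period. Two adjacent lost visits fail all five only at Weeks 40/42 or 42/44, which is 2 of 10 possible positions.

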**Dose Titration Criteria (for Both Study Drug and Reference Therapy):**

Doses should be taken morning and evening, approximately 12 hours apart and without regards to food.

Dose escalations up to the maximum allowed dose for ruxolitinib (25 mg BID) and anagrelide (2.5 mg BID) are permitted. When modifications are made to the ruxolitinib dose, the dose of anagrelide will be modified concurrently. A dose increase of 5 mg BID up to a maximum dose of 25 mg BID is permitted after 2 weeks of treatment for ruxolitinib, and a dose increase of 0.5 mg/day per week up to a maximum dose of 2.5 mg BID is permitted for anagrelide.

Each dose escalation must be at least 1 week apart, and subjects must meet all of the following criteria:

1. Platelet count  $\geq 150 \times 10^9/L$ .
2. Hemoglobin  $\geq 9$  g/dL.
3. ANC  $\geq 1500 \times 10^9/L$
4. One or more of the following:
  - a. Platelet count  $> 600 \times 10^9/L$ .
  - b. WBC count  $> 10 \times 10^9/L$ .
  - c. Minimal improvement, no change, or worsening of vasomotor symptoms including headache, lightheadedness, syncope, atypical chest pain, acral paresthesia, livedo reticularis, erythromelalgia, and transient visual disturbances (eg, amaurosis fugax, scintillating scotomata, ophthalmic migraine).

NOTE: Dose decreases or interruptions for safety are required at any time throughout the study in accordance with Protocol requirements.

A maximum of 8 weeks of dose interruption is permitted in the study; subjects who cannot tolerate the study medications must discontinue from the study.

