## 4. INVESTIGATIONAL PLAN

### 4.1. Overall Study Design

[figure not shown]
This is a Phase 2, randomized, double-blind, double-dummy study in subjects with ET who are resistant to or intolerant of HU (according to modified ELN criteria) with a screening platelet count  $\geq 650 \times 10^9/L$  and WBC count  $\geq 11.0 \times 10^9/L$ . Subjects will be randomized in a 1:1 ratio, stratified by JAKV617 mutation status (positive vs negative), platelet count at screening ( $\geq 1000 \times 10^9/L$  or  $< 1000 \times 10^9/L$ ), and prior anagrelide use (yes vs no) to the following 2 treatment groups:

- Group A: ruxolitinib at a dose of 10 mg BID orally and anagrelide-placebo.
- Group B: anagrelide at a dose of 1 mg BID orally and ruxolitinib-placebo.

The study will enroll approximately 120 subjects. Due to block randomization and stratification, the 2 treatment groups may not each contain exactly the targeted number of subjects (n = 60).

Subjects will receive blinded study treatment for 52 weeks. Options for the open-label treatment phase are detailed in Section 4.1.1. All subjects will be followed for safety (eg, reporting of AEs and SAEs) 30 to 37 days after the last dose of blinded study treatment or open-label study treatment. The overall study design is shown in Figure 1.

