## 5.4. Treatment Modifications: Increases, Interruptions, and Adjustments

Subjects randomized to either study group will be receiving both an active drug and a placebo (dummy drug). Neither the investigator nor the subject will know which is the active drug and which is the placebo. Thus, in order to maintain the blind, when dose modification is required, both of the study drugs will be titrated together.

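### The CYP-inhibitor dose reductions name one blinded drug, while the general rule moves both together; the protocol does not say which governs

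*Protocol*

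**What the plan says.** **Joint rule.** The opening of Protocol Section 5.4, which covers increases, interruptions and adjustments, says that "in order to maintain the blind, when dose modification is required, both of the study drugs will be titrated together". It lists no exception. The Synopsis (Dose Titration Criteria) says: "When modifications are made to the ruxolitinib dose, the dose of anagrelide will be modified concurrently". Section 5.4.1 repeats joint titration for dose increases. Section 5.4.2.2 repeats it just before Table 2: "Doses of both study drugs are titrated simultaneously following the guidelines in" that table.

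**Single-drug rule.** Section 5.4.2.3 stands inside the same Section 5.4. For potent CYP3A4 inhibitors, Section 5.4.2.3.1 says that "a dose reduction of approximately 50% for study treatment is appropriate for subjects who take systemic ketoconazole" or similar agents, and then: "This dose reduction should be accomplished by reducing doses of ruxolitinib or ruxolitinib-placebo from BID to QD". For potent CYP1A2 inhibitors, Section 5.4.2.3.2 says: "This dose reduction should be accomplished by reducing doses of anagrelide or anagrelide-placebo from BID to QD". Both sections describe the size of the cut as applying to study treatment, but the instruction names one drug and its placebo. A note in each allows the earlier twice-daily regimen to resume the day after the inhibitor course ends.

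**Cross-reference.** Section 5.6.2 asks sites to avoid potent inhibitors where they can and points back to Section 5.4.2.3 for the reductions. It does not say whether the companion drug changes.

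**The concern.** Each arm takes one active drug and one placebo. When an inhibitor affects only one of the two drugs, the two rules agree on that drug and differ on its companion. In the arm whose active drug is the companion, the site either leaves the active dose alone or cuts it. A CYP3A4 inhibitor raises the question for anagrelide in Group B, and a CYP1A2 inhibitor raises it for ruxolitinib in Group A. Two sites reading the protocol in good faith could give different active doses to comparable subjects.

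There is a second, narrower gap. Table 1 steps down by one dose level, and Table 2 defines levels as pairs. If only one drug has been cut, the subject is no longer on a defined pair, and a further step during the inhibitor course has no stated starting point.

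**Working it through.** **1. Which passages conflict.**
- Section 5.4.2.3.1 changes ruxolitinib or its placebo and is silent on anagrelide. That conflicts with Section 5.4 and with the Synopsis sentence.
- Section 5.4.2.3.2 changes anagrelide or its placebo and is silent on ruxolitinib. That conflicts with Section 5.4 only, because the Synopsis sentence is triggered by a ruxolitinib change and does not run the other way.

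**2. The plan's own figure.** The protocol gives a reduction of about 50%, reached by going from BID to QD. Cut = 1 − (retained single dose ÷ daily total). At the starting level ("Group A: ruxolitinib at a dose of 10 mg BID orally and anagrelide-placebo"; Group B takes anagrelide 1 mg BID), ruxolitinib gives 1 − 10/20 = 50% and anagrelide 1 − 1/2 = 50%. The stated figure is reproduced.

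**3. All Table 2 levels** (ruxolitinib/anagrelide, mg/day; Week 2 of each level where the weeks differ).

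| Level | Pair | Ruxolitinib QD (cut) | Anagrelide QD (cut) | Table 2 row if both are cut |
|---|---|---|---|---|
| DL 4 | 50/5 | 25 (50%) | 2.5 (50%) | none |
| DL 3 | 40/4 | 20 (50%) | 2 (50%) | DL 1 |
| DL 2 | 30/3 | 15 (50%) | 1.5 (50%) | DL -1 |
| DL 1 | 20/2 | 10 (50%) | 1 (50%) | DL -2 |
| DL -1 | 15/1.5 | 10 or 5 (33% or 67%) | 1 or 0.5 (33% or 67%) | DL -2 or DL -3 |
| DL -2 | 10/1 | 5 (50%) | 0.5 (50%) | DL -3 |
| DL -3 | 5/0.5 | 5 (0%, already QD) | 0.5 (0%) | unchanged |

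The row match is on daily totals. In Week 1 of DL 2 to DL 4 the two anagrelide doses are unequal, so the anagrelide cut depends on which dose is dropped:
- DL 4 (2 + 2.5 mg): 1 − 2/4.5 = 56%, or 1 − 2.5/4.5 = 44%.
- DL 3 (1.5 + 2 mg): 1 − 1.5/3.5 = 57%, or 1 − 2/3.5 = 43%.
- DL 2 (1 + 1.5 mg): 1 − 1/2.5 = 60%, or 1 − 1.5/2.5 = 40%.

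**4. Active dose in the arm without the interacting drug, at DL 1.**
- Group B with a potent CYP3A4 inhibitor: anagrelide 2 mg/day if only ruxolitinib-placebo is cut, 1 mg/day if both are cut.
- Group A with a potent CYP1A2 inhibitor: ruxolitinib 20 mg/day if only anagrelide-placebo is cut, 10 mg/day if both are cut.

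The joint figures are the same whether the once-daily change is mirrored or the companion dose is read from the matching Table 2 row (DL -2, 10/1).

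**5. Position during the course.** After a single-drug cut at DL 1 the pair is 10/2 or 20/1 mg/day, and neither is a Table 2 row. The same holds at every level except DL -3, where nothing changes. A one-level step during the course is therefore undefined under the single-drug reading.

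**6. Link to the primary endpoint.** SAP Section 7.2.3.1.1 requires control at 6 of 7 visits in any one of five overlapping periods (Weeks 32–44, 34–46, 36–48, 38–50, 40–52). Suppose every other visit is controlled. Two adjacent uncontrolled visits then defeat all five periods only at Weeks 40/42 or 42/44, which is 2 of the 10 adjacent pairs. Three consecutive uncontrolled visits do so in 3 of 9 positions (starting at Week 38, 40 or 42).

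**The case against.** The best reply is that the specific rule overrides the general one. Each CYP section names a single drug-and-placebo pair, Section 5.4.2.3.1 ties its cut to ruxolitinib exposure, and Section 5.6.2 sends sites there. The reading is plausible, but the text never states it. The reference to study treatment pulls the other way: Section 5.4.3.2 uses that term with ruxolitinib, anagrelide and matching placebo in parentheses. Nor can the opening of Section 5.4 be confined to efficacy increases, since it speaks of dose modification under a heading that includes adjustments.

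Other parts of the reply stand, and they limit the point.
- Reach is probably small. Exclusion criterion 16 bars potent CYP3A4 inhibitors and CYP1A2 inhibitors around entry, including anticipated use on study. Section 5.6.2 discourages potent inhibitors on study. Section 5.6.3 prohibits QT-prolonging drugs, and Appendix J lists ketoconazole, clarithromycin and ciprofloxacin among them.
- The return to the previous regimen after the course is defined, so only changes during the course are open.
- SAP Sections 6.4 and 6.5 work from the dose actually taken and from a prescribed dose that accounts for modifications. What each subject received is recorded.

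A reader might infer that the single-drug rule unblinds treatment. It does not: in both arms it is applied to active drug or placebo alike. A reader might also infer that responders will be lost and the primary comparison biased. The documents do not support that. They give no number of users and no dose-response for the endpoint, and step 6 shows that a short lapse defeats response only near Weeks 40 to 44 when the other visits are controlled. In Group B the assumed response is 5%, or 0.05 × 60 = 3 subjects, which leaves few responses to lose.

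**Conclusion.** The inconsistency is real, and no passage resolves it. Section 5.4.2.3.1 conflicts with Section 5.4 and the Synopsis; Section 5.4.2.3.2 conflicts with Section 5.4 alone. The active dose in the arm without the interacting drug is unchanged under one reading and cut under the other. The cut is half at most Table 2 levels, but a flat two-fold difference would overstate it: halving fails at DL -1 and DL -3 for both drugs, and in Week 1 of DL 2 to DL 4 for anagrelide. A dose-level step during the inhibitor course also lacks a defined starting pair under the single-drug reading.

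The reach is minor. That judgement rests on the entry exclusion, the advice to avoid these drugs and the QT prohibition, not on a count of users. No effect on the response rate is claimed, and this review takes no position on which dosing rule is right.

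**What to change.** Reconcile the Synopsis (Dose Titration Criteria) and Sections 5.4, 5.4.1 and 5.4.2.2 with Sections 5.4.2.3.1, 5.4.2.3.2 and 5.6.2. The revised text should:
- state once whether a CYP-inhibitor reduction applies to one blinded drug or to both;
- if it applies to one, mark it in Section 5.4 and the Synopsis as an exception to the joint rule;
- state how a further Table 1 or Table 2 change is made while the inhibitor is being taken;
- use the same wording in each place, so that the choice is not left to the site.

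The content of the rule is for the sponsor's clinical team. The cost is protocol wording and a site memo, with no new data collection and no change to the analysis.
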